6.9.1 Study Site Retention Samples

Not applicable.

7 DISCONTINUATION OF STUDY INTERVENTION AND PARTICIPANT WITHDRAWAL

7.1 Discontinuation of Study Intervention

Discontinuation of study intervention does not represent withdrawal from the study. As certain data on clinical events beyond study intervention discontinuation may be important to the study, they must be collected through the participant's last scheduled follow-up, even if the participant has discontinued study intervention. Therefore, all participants who discontinue study intervention before completion of the protocol-specified treatment period

will still continue to participate in the study as specified in Section 1.3 and Section 8.1.9, or if available, a PCL. If a participant discontinues at any point during the dosing period, all safety follow-ups and PK, PD sample collections should continue weekly post the last dose. Safety procedures include full physical examination, systemic infusion reaction assessment, semi-recumbent vital signs, orthostatic vital signs, safety lab measurements, AE reviews and assessment of time to hemostasis if on-site dialysis. The poststudy timing and assessments should be performed as outlined in Section 1.3.2

Participants may discontinue study intervention at any time for any reason or be discontinued from the study intervention at the discretion of the investigator should any untoward effect occur. In addition, a participant may be discontinued from study intervention by the investigator or the Sponsor if study intervention is inappropriate, the study plan is violated, or for administrative and/or other safety reasons. Specific details regarding procedures to be performed at study intervention discontinuation are provided in Section 8.1.9.

A participant must be discontinued from study intervention, but continue to be monitored in the study, for any of the following reasons:

- The participant or participant's legally acceptable representative requests to discontinue study intervention.
- The participant has a medical condition or personal circumstance which, in the opinion of the investigator and/or Sponsor, placed the participant at unnecessary risk from continued administration of study intervention.
- The participant has a confirmed positive serum pregnancy test.
- The participant has a positive drug screen at any time during the course of the study and after confirmation by recheck.

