Orthostatic VS	X			X	X	X	X	X	X			X	X						Sec. 8.3.2.2 To be done at predose on Days 1, 3, 5 and 8. To be done before start of dialysis on Days -3 and 15.	
12-lead ECG	X			X	X	X	X	X	X		X					X		Sec. 8.3.3 To be done at predose on Days 1, 3, 5 and 8		
Serum FSH - (WONCBP only)	X																			
Serum or Urine Pregnancy test (WOCBP only)	X			X													X			
HIV, hepatitis B and C screen	X																			
Drug Screen and Alcohol Breath Test	X				X														Appendix 2 DS and alcohol breath test is mandatory at Screening and predose; any additional DS and alcohol breath tests are conducted per site SOP Blood or saliva DS may be used for anuric participants	

Study Period:	Screen-ing	Run-in ^a													Intervention					Intervention Notes
		Day -14	Day -7	Day -3	Day 1	Day 2	Day 3	Day 5	Day 8	Day 9	Day 10	Day 12	Day 15	Day 21	Day 29	Day 35	Day 49	Day 67	Day 104	
Scheduled Day																				
Hematology	X			X	X		X		X		X		X		X	X	X	X	X	Sec. 8.3.5 Appendix 2 To be done predose on Days 1, 3 and 8
aPTT/PT at Local Lab	X				X		X	X	X	X	X	X	X	X	X		X		X	Sec. 8.3.5 Appendix 2 Days 1, 3, 5 & 8: predose, 1h and 12h.
Chemistry ^c	X			X	X		X		X		X		X		X	X	X	X	X	Sec. 8.3.5 Appendix 2 To be done at predose on Days 1, 3 and 8
Hemoccult Test ^d				X		X		X	X		X		X		X		X			Sec. 8.3.5, 8.11.5
AE/SAE review	X	X	X	X	X	X	X	X	X	X	X	X	X	X	X	X	X	X	X	Sec 8.5, Appendix 3
Pharmacokinetics																				
Blood for Plasma MK-2060 Assay ^{e,f}					X	X	X	X	X	X	X	X	X	X	X	X	X	X	X	Sec. 8.7 Days 1 & 8: predose, 1h, 12h. Days 3 &5: predose, 1h. See footnotes e, f
Blood for Clopidogrel Assay ^{e,f}		X	X	X	X	X	X	X	X											Sec. 8.7 See footnote e, f.
Pharmacodynamics																				
Blood for PT/aPTT/ FXI Activity by Central Lab ^f					X	X	X	X	X	X	X	X	X	X	X	X	X	X	X	Sec. 8.8, Days 1 & 8: predose and 1h (within 15 min of end of infusion). Days 3 &5: predose
Biomarkers																				
Blood for Plasma ADA ^f					X								X			X		X	X	Sec. 8.9.3 Day 1: predose
Blood (DNA) for Planned Genetic Analysis					X															See section 8.8

Study Period: Scheduled Day	Screen-ing	Intervention													Post-study	Intervention Notes			
		Day -14	Day -7	Day -3	Day 1	Day 2	Day 3	Day 5	Day 8	Day 9	Day 10	Day 12	Day 15	Day 21	Day 29	Day 35	Day 49	Day 67	Day 104

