- COVID-19 vaccine may be administered. Study intervention must be given at least 72 hours following or at least 48 hours prior to any COVID-19 vaccination. Investigational COVID-19 vaccines (i.e., those not licensed or approved for Emergency Use) are not allowed.

Prior/Concurrent Clinical Study Experience

18. Participated in another investigational study within 4 weeks (or 5 half-lives, whichever is greater) prior to the screening visit. The window will be derived from the date of the last dose in the previous study.

Diagnostic Assessments

19. Has a blood pressure >190 mmHg systolic or >110 mmHg diastolic.

20. Exclusion criteria for ECG:

- Heart rate < 40 or > 110 bpm
- QTc interval > 500 msec
- Any significant arrhythmia or conduction abnormality, (including but not specific to atrioventricular block [2nd degree or higher], Wolff Parkinson White syndrome [unless curative radio ablation therapy]), which, in the opinion of the investigator and sponsor, could interfere with the safety for the individual patient.

Other Exclusions

21. Under the age of legal consent.

22. Consumes greater than 3 servings of alcoholic beverages (1 serving is approximately equivalent to: beer [354 mL/12 ounces], wine [118 mL/4 ounces], or distilled spirits [29.5 mL/1 ounce]) per day. Participants who consume 4 servings of alcoholic beverages per day may be enrolled at the discretion of the investigator.

23. Consumes excessive amounts, defined as greater than 6 servings (1 serving is approximately equivalent to 120 mg of caffeine) of coffee, tea, cola, energy drinks, or other caffeinated beverages per day.

24. A regular user of cannabis, any illicit drugs or has a history of drug (including alcohol) abuse within approximately 2 years. Participants must have a negative drug screen prior to treatment allocation. Participants with a positive drug screen due to the use of

physician prescribed medications (e.g., opioids, benzodiazepines, antidepressants) may be enrolled at the discretion of the investigator. In addition, participants with a positive THC may be enrolled at the discretion of the investigator if the participants' THC use is under 4 times/month and the participants agree to not use during their study participation. Participants with positive THC on screening may have rechecks performed at the discretion of the investigator to ensure compliance with abstinence from THC use during study participation.

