6.4 Study Intervention Compliance

Interruptions from the protocol-specified treatment plan require consultation between the investigator and the Sponsor and written documentation of the collaborative decision on participant management.

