6.5 Concomitant Therapy

Medications or vaccinations specifically prohibited in the exclusion criteria are not allowed during time periods specified by this protocol for that medication or vaccination. If there is a clinical indication for any medications or vaccinations specifically prohibited, discontinuation from study intervention may be required. The investigator should discuss any questions regarding this with the Sponsor Clinical Director. The final decision on any supportive therapy or vaccination rests with the investigator and/or the participant's primary physician. However, the decision to continue the participant on study intervention requires the mutual agreement of the investigator, the Sponsor, and the participant.

Any medication or vaccine (including over-the-counter or prescription medicines, vitamins, and/or herbal supplements or other specific categories of interest) that the participant is receiving at the time of enrollment or receives during the study must be recorded along with:

- Reason for use
- Dates of administration including start and end dates
- Dosage information including dose and frequency

The Sponsor Clinical Director should be contacted if there are any questions regarding concomitant or prior therapy.

Concomitant use of the following medications will be allowed during the conduct of the study as long as the subject has been on a stable dose and treatment regimen for at least approximately 2 weeks prior to screening and is able to withhold the use within four hours

prior to administration of the first dose of study drug. The name (generic and brand), dose and regimen for all concomitant medications should be recorded on the appropriate CRF.

All medications must be reviewed and approved by the Sponsor clinical monitor prior to enrollment of an individual patient. This list is not exhaustive, but serves as a guideline to facilitate the approval process between the investigator and the Sponsor clinical monitor

ALLOWED MEDICATIONS

Lipid Lowering Agents: Statins

Atorvastatin
Simvastatin
Pravastatin
Lovastatin
Rosuvastatin
Pravastatin

Lipid Lowering Agents: Fibrates

Fenofibrate
Gemfibrozil

Lipid Lowering Agents: Other

Ezetimibe

Anti-Hypertensive Medications:

Monotherapy and combination therapy with an angiotensin converting enzyme (ACE) inhibitor, an angiotensin II receptor antagonist, beta blockers, calcium channel blockers, or a diuretic is allowed in the study.

Specific therapeutic categories include:

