10.2 Appendix 2: Clinical Laboratory Tests

- The tests detailed in [Table 8](#) will be performed by the local laboratory.
- Protocol-specific requirements for inclusion or exclusion of participants are detailed in Section 5 of the protocol.
- Additional tests may be performed at any time during the study as determined necessary by the investigator or required by local regulations.

Table 8 Protocol-required Safety Laboratory Assessments

Laboratory Assessments	Parameters							
Hematology	Platelet Count	RBC Indices: MCV MCH Reticulocytes	WBC count with Differential: Neutrophils Lymphocytes Monocytes Eosinophils Basophils					
	RBC Count							
	Hemoglobin							
	Hematocrit							
Chemistry ^a	BUN	Potassium	AST/SGOT	Total bilirubin (and direct bilirubin, if total bilirubin is above the ULN)				
	Albumin	Bicarbonate	Chloride	Phosphorous				
	Creatinine	Sodium	ALT/SGPT	Total Protein				
	Glucose	Calcium	Alkaline phosphatase					
Other Screening Tests	
• aPTT, PT (collection according to the trial schedule of activities Section 1.3 for aPTT and PT collected at local lab)• FSH (as needed in WONCBP only)• Serum or urine β human chorionic gonadotropin (β hCG) will be carried out on Day 1 predose. At all other timepoints urine or serum pregnancy test will be carried out (as needed for WOCBP) (Serum β hCG pregnancy test will be carried out if there is a positive urine test)• alcohol breath test and drug screen (to include at minimum: amphetamines, cocaine, opiates, cannabinoids and benzodiazepines)• Serology (HIV antibody, HBsAg, and hepatitis C virus antibody)]							
ALT=alanine aminotransferase; AST=aspartate aminotransferase; BUN=blood urea nitrogen; FSH=follicle-stimulating hormone; [HBsAg=hepatitis B surface antigen]; hCG=human chorionic gonadotropin; [HIV=human immunodeficiency virus]; MCH=mean corpuscular hemoglobin; MCV=mean corpuscular volume; RBC=red blood cell; SGOT=serum glutamic-oxaloacetic transaminase; SGPT=serum glutamic-pyruvic transaminase; ULN=upper limit of normal; WBC=white blood cell; WOCBP=women of childbearing potential; WONCBP=women of nonchildbearing potential								
^a Fasting: Participants should fast for at least 4 hours prior to glucose measurement.								

The investigator (or medically qualified designee) must document their review of each laboratory safety report.

10.3 Appendix 3: Adverse Events: Definitions and Procedures for Recording, Evaluating, Follow-up, and Reporting

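### Section 7.1 requires MK-2060 to be stopped for any confirmed positive drug screen, with no exception for a prescribed-medication positive that exclusion criterion 24 accepts at entry

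*Combined protocol and SAP*

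**What the plan says.** Section 7.1 gives a list of events after which the participant must come off study intervention while remaining in follow-up. One is "The participant has a positive drug screen at any time during the course of the study and after confirmation by recheck". The wording leaves no discretion and names no exempt cause.

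Exclusion criterion 24 in Section 5.2 starts from a negative screen before allocation and then relaxes it in two ways:

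- A positive caused by "physician prescribed medications (e.g., opioids, benzodiazepines, antidepressants) may be enrolled at the discretion of the investigator".
- A THC positive may be accepted if "THC use is under 4 times/month and the participants agree to not use during their study participation". For these participants the investigator "may have rechecks performed at the discretion of the investigator to ensure compliance with abstinence from THC use during study participation".

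The Schedule of Activities (Section 1.3) marks the drug screen at Screening and Day 1 predose only; "any additional DS and alcohol breath tests are conducted per site SOP". Appendix 2 sets the panel: "drug screen (to include at minimum: amphetamines, cocaine, opiates, cannabinoids and benzodiazepines".

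Two other provisions bear on the point. Section 6.5 says "All medications must be reviewed and approved by the Sponsor clinical monitor prior to enrollment of an individual patient". Section 6.4 says "Interruptions from the protocol-specified treatment plan require consultation between the investigator and the Sponsor".

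**The concern.** The entry rule and the stopping rule treat the same finding differently. Criterion 24 treats a positive explained by a prescription as acceptable. Section 7.1 treats any confirmed positive as a reason to stop, whatever its explanation. The confirmatory recheck does not help, because for someone still taking the medication it would confirm the known cause.

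The regimen was chosen to observe bleeding while MK-2060 exposure and FXI inhibition are at their highest (Section 4.3.1). At most 12 participants are allocated. One who is stopped early for a reason already accepted at entry stays in the All Subjects as Treated population (Section 9.5). That participant then counts in the bleeding-AE summary with less exposure than intended. Because additional screens depend on site SOP and the study is multi-site, two similar participants could also be handled differently.

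**Working it through.** **Step 1: can an accepted positive recur?** Criterion 24 names opioids, benzodiazepines and antidepressants. The minimum panel includes opiates and benzodiazepines but no antidepressant class, so the overlap that matters is prescribed opioids and benzodiazepines. A participant who was positive at entry and stays on the same medication would be expected to be positive again on the same panel.

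**Step 2: when can 7.1 act?** Doses are given on Days 1, 3, 5 and 8 (Table 3). The rule can withhold a dose only if a further screen falls after the Day 1 dose and before the Day 8 dose. Scheduled screens in that window: none. Criterion 24's discretionary rechecks concern THC only, so for prescribed medication the only stated route is an extra screen under site SOP. A stop in the window leaves 1, 2 or 3 of 4 doses given.

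**Step 3: how much exposure is lost?** Inputs are the preliminary geometric means for MK-2060-004 Part 2 in Table 2: Day 1 Cmax 32.4 nM, Day 8 predose 47.1, Day 8 end of infusion 91.4, Day 15 predose 44.7.

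*Stop after one dose, using observed values only:* 32.4 / 91.4 = 0.354, so the peak is about 35% of the Day 8 end-of-infusion level.

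*Stop after two or three doses.* These are not tabulated. Assume superposition with mono-exponential decline and an equal increment I per dose, with k chosen so that I × (e^(-7k) + e^(-5k) + e^(-3k)) = 47.1.

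- (a) I = 32.4 gives k = 0.151/day. Peak after two doses: 32.4 × (1 + e^(-2k)) = 56.4 nM, or 62% of 91.4. Peak after three: 32.4 × (1 + e^(-2k) + e^(-4k)) = 74.1 nM, or 81%.
- (b) I = 91.4 - 47.1 = 44.3 gives k = 0.220/day. The same formulas give 72.8 nM (80%) and 91.2 nM (100%).

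*Day 15 level if the Day 8 dose is omitted.* Under mono-exponential decline the factor e^(-7k) cancels, so the ratio without to with the dose equals the Day 8 predose level divided by the Day 8 post-dose level.

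- (a) 47.1 / (47.1 + 32.4) = 47.1 / 79.5 = 59%.
- (b) 47.1 / 91.4 = 52%.
- Observed decline from Day 8 end of infusion to Day 15 predose: k = ln(91.4 / 44.7) / 7 = 0.102/day. Without the dose, 47.1 × 44.7 / 91.4 = 23 nM, against 44.7 nM observed with it, again 52%.

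**Step 4: how often?** The documents give neither the number of participants enrolled on such medication nor any site's screening practice. If p is the assumed chance that a given participant is an accepted prescription positive, is screened again and is confirmed positive while doses remain, then P(at least 1 of 12) = 1 - (1 - p)^12. That is 5.8% at p = 0.005, 21.5% at p = 0.02 and 71.8% at p = 0.10. The spread shows only that the documents cannot settle the frequency.

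**The case against.** The case for leaving the text alone is that the problem may never arise. No screen is scheduled after Day 1, and the prescribed-medication route depends on site SOPs that are not in the documents. The Sponsor clinical monitor approves each participant's medications before enrolment, so a later positive would be anticipated. Interruptions of treatment also require consultation with the Sponsor. If a stop did occur, safety, PK and PD follow-up would continue (Section 7.1), and a replacement could be enrolled within 21 days of first dosing (Section 5.5). The AE analysis is descriptive (Section 9.6), so no test or threshold for it changes. All of this stands and fixes the size of the point as small. None of it supplies the missing exception: approval at entry and consultation on interruptions leave a mandatory stop mandatory.

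Three stronger readings are tempting and are not supported.

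- *That THC positives raise the same conflict.* Criterion 24 accepts THC only with agreed abstinence and provides rechecks to enforce it. Stopping on a later confirmed THC positive is consistent with that condition. The documents also give no level or washout time by which an investigator could separate use before entry from use after it.
- *That 7.1 stops people at the Day 1 predose screen.* Taken literally, its time span reaches that far. But criterion 24 governs screens before allocation, allocation follows completion of predose procedures (Section 8.11.2), and no MK-2060 has yet been given.
- *That omitting the Day 8 dose cuts the Day 15 level to 23-37% of normal.* That range comes from dividing modelled values of 10.1-16.4 nM by the observed 44.7 nM. With the Day 8 dose included, the same two models predict only 19.6-27.6 nM on Day 15, so they decline too fast over that week. The comparison must be made within one model or on the observed decline.

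**Conclusion.** The conflict is real and confined to positives explained by a prescribed medication accepted under criterion 24. For those participants, a further screen before Day 8 would trigger a mandatory stop for a reason the investigator had already considered and accepted.

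The effect is contingent and small. The worst case is a stop after one dose, at about 35% of the Day 8 end-of-infusion level, taken from observed geometric means in another study. After three doses little peak exposure is lost (81-100%), and the Day 15 level is about 52-59% of what it would have been. The two- and three-dose figures rest on superposition and mono-exponential decline; the peak figures also rest on an assumed equal increment per dose, and the Day 15 figure falls to its lower end, about 23 nM, on the observed decline. No frequency is claimed, and no planned conclusion is shown to change. This is a cheap improvement, not a defect that threatens the study.

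**What to change.** Keep the 7.1 bullet and add at its end: *except where the investigator documents that the positive is explained by a physician-prescribed medication accepted under exclusion criterion 24.*

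Confirmed positives for THC and for every other cause would still require discontinuation. Section 5.2 needs no change. The cost is one clause, plus a short investigator note each time the exception is used. Visits, samples, sample size and analysis are unaffected.

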7.2 Participant Withdrawal From the Study

A participant must be withdrawn from the study if the participant or participant's legally acceptable representative withdraws consent from the study.

If a participant withdraws from the study, they will no longer receive study intervention or be followed at scheduled protocol visits.

Specific details regarding procedures to be performed at the time of withdrawal from the study, as well as specific details regarding withdrawal from FBR, are outlined in Section 8.1.9. The procedures to be performed should a participant repeatedly fail to return for scheduled visits and/or if the study site is unable to contact the participant are outlined in Section 7.3.

7.3 Lost to Follow-up

If a participant fails to return to the clinic for a required study visit and/or if the site is unable to contact the participant, the following procedures are to be performed:

- The site must attempt to contact the participant and reschedule the missed visit. If the participant is contacted, the participant should be counseled on the importance of maintaining the protocol-specified visit schedule.
- The investigator or designee must make every effort to regain contact with the participant at each missed visit (eg, telephone calls and/or a certified letter to the participant's last known mailing address or locally equivalent methods). These contact attempts should be documented in the participant's medical record.
- Note: A participant is not considered lost to follow-up until the last scheduled visit for the individual participant. The missing data for the participant will be managed via the prespecified statistical data handling and analysis guidelines.

8 STUDY ASSESSMENTS AND PROCEDURES

- Study procedures and their timing are summarized in the SoA.
- Adherence to the study design requirements, including those specified in the SoA, is essential and required for study conduct.
- The investigator is responsible for ensuring that procedures are conducted by appropriately qualified (by education, training, and experience) staff. Delegation of study-site personnel responsibilities will be documented in the Investigator Trial File Binder (or equivalent).
- All study-related medical decisions must be made by an investigator who is a qualified physician.
- All screening evaluations must be completed and reviewed to confirm that potential participants meet all eligibility criteria. The investigator will maintain a screening log to record details of all participants screened and to confirm eligibility or record reasons for screening failure, as applicable.
- Procedures conducted as part of the participant's routine clinical management (eg, blood count) and obtained before signing of ICF may be used for screening or baseline purposes provided the procedure met the protocol-specified criteria and were performed within the time frame defined in the SoA.
- Additional evaluations/testing may be deemed necessary by the investigator and or the Sponsor for reasons related to participant safety. In some cases, such evaluation/testing may be potentially sensitive in nature (eg, HIV, hepatitis C), and thus local regulations may require that additional informed consent be obtained from the participant. In these cases, such evaluations/testing will be performed in accordance with those regulations.

The maximum amount of blood collected from each participant over the duration of the study will not exceed ~453 mL (Appendix 8).

Repeat or unscheduled samples may be taken for safety reasons or for technical issues with the samples.

